Procedure: Sessions will be conducted in the afternoons, in comfortable rooms at the Human Behavioral Pharmacology Laboratory. At each visit, participants will provide breath (Alco-sensor III, Intoximeters, St. Louis, MO) and urine (ToxCup, Branan Medical Co. Irvine, CA) samples to detect recent drug use or pregnancy (women; Aimstrip, Craig Medical Vista, CA). Positive pregnancy tests will result in exclusion and positive drug tests will result in rescheduling or exclusion. All sessions will be conducted from 3 pm to 8 pm, and will be separated by at least 48 hours but no more than 7 days. Upon arrival pre-beverage mood and vital signs will be recorded, and beverage administrations will occur 30 min after arrival, at 3:30pm. Mood and vital signs will be recorded every 30 minutes post-beverage administration. Between measurements in the laboratory, participants may read or watch movies from an approved list, but will not be allowed to sleep or have access to internet or cell phones. Data collection will end at 8pm and participants will be provided with a snack and discharged providing they pass a sobriety test and breath alcohol concentrations are below 0.02mg% (as per NIAAA guidelines). If BrAC is above 0.02%, BrAC samples will be collected every 15 minutes until BrAC is below 0.02mg% after which participants will be allowed to leave. However, participants will not be allowed to drive themselves home. If using public transportation, participants will be accompanied by a lab member to the bus stop, and funds for public transportation will be given, if needed. If they are getting picked up, a lab member will wait with them until their ride arrives. Participants will be made aware of these travel requirements at their orientation session. In addition, we will confirm travel arrangements with the participant prior to drink administration at each of the sampling and choice sessions.

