Statistical analyses: First, we will check that the high and low impulsive groups are matched on sex, race, education, SES, cigarette smoking, alcohol drinking and other drug use. To test the hypothesis that individuals high in impulsive action will report significantly greater stimulation and euphoria after alcohol than those low in impulsive action, we will conduct 2 (Group) X 2 (Drug) mixed design analyses of variance (ANOVA), with dose order and sex included as covariates, for each of the subjective response measures (i.e., BAES, ARCI, and DEQ). Group (high or low impulsive action) will be the between-subjects factor, and will be determined at the orientation session (see above). The dependent measures of subjective stimulation and

euphoria will be calculated as area under the curve (AUC). An average AUC across the two alcohol sessions will be calculated, and an average AUC across the two placebo sessions will be calculated. If the overall F-test for the group X drug interaction is significant ($p < .05$), post hoc paired t-tests will be used to test for drug effects (relative to placebo) in the high and low impulsive action groups separately. To test the hypothesis that high impulsive individuals will exhibit greater preference for alcohol over placebo compared to low impulsive individuals, we will compare choice for alcohol or placebo in high and low impulsive individuals. We will perform a chi-square analysis to determine if the high impulsive action group is comprised of a higher number of choosers compared to the low impulsive action group, and a between-groups t test to see if the high impulsive action group chooses a greater number of alcohol servings than the low impulsive action group.

Sample size determination: Estimations of sample size were derived from our preliminary data with d-amphetamine. Between groups (high vs. low impulsive action) t tests for subjective response measures of Elation and Vigor (AUC; 20 mg vs. placebo) suggest a medium effect size ($d = .60\text{--}.68$). $N=60$ subjects would provide 80% power ($\alpha = .05$) to detect a difference between high and low impulsive individuals.

HUMAN SUBJECTS

Risks to subjects:

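### The plan does not say whether or how the pre-beverage mood rating enters the AUC analysis; adjusting for it could sharpen the Group x Drug test at almost no cost

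*Combined protocol and SAP*

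**What the plan says.** The Procedure section states: "Upon arrival pre-beverage mood and vital signs will be recorded". It continues: "Mood and vital signs will be recorded every 30 minutes post-beverage administration". So each sampling session should yield an arrival rating followed by a series of later ratings. The section does not name the instruments that make up mood.

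The Statistical analyses section sets out a 2 (Group) x 2 (Drug) mixed ANOVA for each subjective measure, "with dose order and sex included as covariates". Stimulation and euphoria "will be calculated as area under the curve (AUC"), and then: "An average AUC across the two alcohol sessions will be calculated, and an average AUC across the two placebo sessions will be calculated". The section does not say which time points enter the AUC, whether the arrival rating is its first point, or whether the area is taken relative to that rating. Baseline mood is not a listed covariate.

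The Sample size determination section claims 80% power with 60 subjects at d = .60 to .68 and alpha .05. These effect sizes come from drug-versus-placebo AUC differences in earlier d-amphetamine data. How baseline was handled in those data is not stated.

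**The concern.** The Group x Drug interaction tests the main subjective-effects hypothesis. With two drug conditions it is a comparison of the alcohol-minus-placebo AUC difference between groups. That difference removes whatever is constant in a person's mood. It does not remove the part that varies from one day to the next, and sessions are 48 hours to 7 days apart. If a subject happens to arrive more energetic on alcohol days than on placebo days, an AUC that ignores arrival mood carries that chance difference into the error term.

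Two things are at stake. The first is precision in a test that has little to spare. The second is clarity: an uncorrected AUC, a baseline-subtracted AUC and a baseline-adjusted AUC are three different analyses of the same outcome. They can have quite different power, and the current text is compatible with more than one of them.

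**Working it through.** **Inputs.** From the documents: 30 per group (Design); d = .60 to .68, alpha .05 and claimed power 80% (Sample size determination); covariates and AUC averaging (Statistical analyses). Not in the documents: r, the correlation between the alcohol-minus-placebo difference in arrival score and the alcohol-minus-placebo difference in AUC. It is varied as an assumption.

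**Step 1: the plan's own figure.** The interaction F-test has 1 numerator degree of freedom, so it equals a two-sided t test on the AUC difference. With n = 30 per group, the noncentrality is d x sqrt(n/2) = d x sqrt(15), on 58 degrees of freedom.

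- d = .60: .60 x 3.873 = 2.32, power 62.8%.
- d = .68: .68 x 3.873 = 2.63, power 73.6%.

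The stated 80% is not reproduced two-sided; 60 subjects reach it only at d = .736. A one-sided test reaches 80% at d = .65, but that does not match an F-test at .05. This gives the starting point for what follows.

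**Step 2: baseline contrast as covariate.** The covariate reduces residual variance by the factor 1 - r², so the effective effect size is d / sqrt(1 - r²), with one further degree of freedom spent. This assumes that d was obtained from AUC not already corrected for baseline.

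| r | variance removed | effective d (.60 / .68) | power (.60 / .68) |
|---|---|---|---|
| 0 | 0% | .600 / .680 | 62.7% / 73.5% |
| .2 | 4% | .612 / .694 | 64.5% / 75.3% |
| .3 | 9% | .629 / .713 | 66.8% / 77.5% |
| .4 | 16% | .655 / .742 | 70.3% / 80.6% |
| .5 | 25% | .693 / .785 | 75.1% / 84.8% |

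Against Step 1, the gain is 1.7 points at r = .2 (64.5 - 62.8 and 75.3 - 73.6), about 4 points at r = .3, and 11 to 12 points at r = .5. At r = 0 the loss is about 0.1 point. Reaching 80% would need r of about .58 at d = .60, or .38 at d = .68.

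**Step 3: simple subtraction instead.** Let A be the AUC contrast and B the baseline contrast on a common scale. Then Var(A - B) = SD_A² + SD_B² - 2 r SD_A SD_B. This exceeds SD_A² whenever r < SD_B / (2 SD_A), which is .5 if the SDs are equal. With equal SDs the effective effect size is d / sqrt(2 - 2r):

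- r = .3: .507 / .575, power 48.9% / 59.1%.
- r = .5: .600 / .680, power 62.8% / 73.6% (no gain).

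So at r = .3 and d = .60 the choice of form moves power from about 49% (subtracted) through 63% (uncorrected) to 67% (covariate).

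**The case against.** A reader might infer that the plan discards the arrival rating and analyses a raw AUC. The documents do not support that. They leave the AUC undefined with respect to baseline, and an area measured from the arrival value would be consistent with the text. What stands is that no use is specified.

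A reader might also infer that the result would be biased. It would not be on this account: the initial drug is randomised and sessions alternate, so arrival mood has no systematic reason to differ between alcohol and placebo days. Only precision is affected.

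The gain itself is uncertain. Much of the mood variance has already cancelled in the contrast or been averaged down over two sessions, and nothing in the documents sizes what remains. If r is below .2, the gain is under 2 points. If the preliminary effect sizes came from baseline-corrected AUC, the reduction is already inside d and counting it again would be wrong. These objections stand as limits on the size of the point.

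Scope is limited too. DEQ Drug Liking rates a drug effect and has no natural pre-beverage counterpart. The Procedure section does not confirm that BAES and ARCI are among the arrival ratings.

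Finally, the gap between 63-74% and the claimed 80% is a sample-size matter that exists whatever is done about baseline. It should not be read as caused by the missing adjustment, nor the adjustment as a cure for it.

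**Conclusion.** The point holds as an incomplete outcome definition and a missed, nearly free gain in precision. The gain ranges from nothing, if r is near zero or d is already baseline-corrected, to about 4 points at r = .3 and 11 to 12 points at r = .5. These figures assume a two-sided test, 30 analysed per group, the plan's own d taken from uncorrected AUC, and a value of r that the documents do not supply. The balance favours the covariate because its worst case is negligible. The validity of the Group x Drug test is not in question.

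**What to change.** In the Statistical analyses section:

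- State the time points and reference level of the AUC, and compute it from post-beverage ratings only.
- For BAES and ARCI, average the arrival score over the two alcohol sessions and over the two placebo sessions. Test Group on the alcohol-minus-placebo AUC difference, with the alcohol-minus-placebo difference in averaged arrival score as a covariate, alongside dose order and sex.
- If a mixed model is kept, enter each condition's arrival score as a deviation from the person's own mean, and enter that mean as a separate term. A single condition-specific covariate blends between-person and within-person associations and is not in general the same analysis.
- Exempt the DEQ drug-effect items, and do not use simple change from baseline as the main form.

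The Procedure section should name the instruments given on arrival. The Sample size determination section should say whether the preliminary AUC was baseline-corrected.

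The cost is a few sentences and one model degree of freedom in the difference analysis. No new data are needed if BAES and ARCI are already given before the beverage; if they are not, they would have to be added to the arrival ratings.

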Design: The study will use a between-subjects design to test two measures of reward (subjective effects and drug choice) in participants pre-selected based on their performance on the stop task (Logan et al., 1997), a standardized measure of impulsive action. Participants will be eligible to participate if they score in the upper (stop reaction time > 325ms; N=30) or lower (stop reaction time < 270ms; N=30) quartiles on stop task performance (calculated from over 500 previous subjects in our lab) during the screening session. Subjects will then participate in a 5-session choice procedure, consisting of 4 sampling sessions and one choice session. During the sampling sessions, participants will consume beverages containing 0.8 g/kg ethanol (divided into 4 servings of 0.2 g/kg each) or a matching placebo under double blind conditions. During the choice session, they will choose the beverage they prefer, and drink the number of servings (from 1-4) they prefer. The primary outcome measures are subjective ratings of stimulation, drug liking, "euphoria", and "arousal" (see below) on the sampling sessions, and choice and number of servings of alcohol or placebo on the choice session.

Participants: Healthy male and female volunteers, aged 21-29, will be recruited by posters, advertisements, and word-of-mouth referrals. Participants will provide consent under Protocol #13681B to undergo the screening procedure, which will include an EKG, physical exam, clinical psychiatric interview, and stop task performance. Participants will be moderate drinkers (7-30 drinks per week) who report at least one binge drinking episode (5 or more drinks on a single occasion for men; 4 for women) in the last month. Asian subjects who report a pronounced 'flushing' reaction will be excluded. Subjects who smoke >5 cigarettes/day will be excluded to avoid acute nicotine effects or withdrawal during the sessions. Additional exclusion criteria include any serious medical problems, Axis I psychiatric disorders including substance dependence (APA, 1994), pregnancy or lactation (females), lack of a high school education, and lack of fluency in English. Women not currently using hormonal contraceptives will only be tested during the follicular phase (days 1-14; White et al., 2002). We will monitor participant

characteristics throughout the study to ensure that the high and low impulsive groups are matched on sex, race, education, SES, alcohol drinking, cigarette smoking, and other drug use.

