Orientation Session: Subjects will attend an orientation session during which study procedures are explained, and trait impulsive action is re-assessed. They will read and sign the consent form, complete self-report questionnaire measures of personality, and perform the stop task. Subjects will also perform additional behavioral impulsivity tasks, including a go/no-go task and a delay discounting task, to determine the specificity of these effects to impulsive action and the stop task. Finally, they will complete a sweet taste test to examine associations between alcohol reward and a non-drug reward.

Sampling Sessions: During the four sampling sessions, subjects will undergo the pre-session screening procedures described above, and then on each of four sessions they will receive 4 color-coded beverages in green or blue cups, containing alcohol (0.2 g/kg per dose, total dose

0.8 g/kg) or placebo. Within each session all the beverages will contain either alcohol or placebo, and the alcohol or placebo sessions will be scheduled in alternating order, with the initial drug randomized. For each subject the alcohol beverages will be in cups of one color, and the placebo in cups of the other color. Alcohol and placebo color-coding will be randomized across subjects. Subjects will be told that the drug and dose in each color will be the same on both days, and instructed to pay close attention to the color of the beverage container and to associate the color with how the drug makes them feel.

Choice Session: During the choice session, subjects will undergo pre-session screening and then complete an alcohol purchase task in which they choose between varying amounts of money and each color cup. The subject will then choose the color of the beverage cup they prefer (i.e., green or blue) to ingest and the number of servings they would like to consume (1-4). Mood and physiological measures will be obtained at regular intervals but the primary outcome measures will be whether they choose alcohol over the placebo, and the number of servings they choose to drink.

Measures:

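### Minor, low-cost improvement: carry the sex adjustment already planned for the subjective-effect ANOVAs over to the two primary choice tests

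*Combined protocol and SAP*

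**What the plan says.** The Statistical analyses section specifies Group by Drug ANOVAs "with dose order and sex included as covariates, for each of the subjective response measures". The choice outcomes are handled differently. For alcohol against placebo the text reads "We will perform a chi-square analysis to determine if the high impulsive action group is comprised of a higher number of choosers", and for quantity it plans "a between-groups t test to see if the high impulsive action group chooses a greater number of alcohol servings". Neither test has a covariate or a stratification factor.

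Both choice outcomes are primary. The Design paragraph lists "choice and number of servings of alcohol or placebo on the choice session" among the primary measures, and the Choice Session paragraph says "the primary outcome measures will be whether they choose alcohol over the placebo, and the number of servings they choose to drink".

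The comparison groups are "participants pre-selected based on their performance on the stop task", so group is not randomised. Balance on sex is sought in two ways. The Participants paragraph says the team will monitor "characteristics throughout the study to ensure that the high and low impulsive groups are matched on sex" and on other factors, and the analysis section opens with "First, we will check that the high and low impulsive groups are matched on sex".

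**The concern.** Randomisation does not balance sex between the high and low impulsive groups, and the plan itself treats sex as worth adjusting for in the subjective outcomes. If men and women differ in how often they choose alcohol or in how many servings they take, any sex imbalance that remains after matching moves the group difference in both choice tests. If matching is exact there is no bias, but the sex effect stays in the error variance of the unadjusted t test, which then loses a little power. In both cases a covariate that is already recorded would help.

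**Working it through.** **Inputs from the documents.** 30 per group (Design); d = 0.60 to 0.68 and alpha 0.05 (Sample size determination).

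**Assumptions, not in the documents.** A sex effect of 0.3 to 0.8 SD on servings, or 20 percentage points on alcohol choice; SD 1 within sex; two-sided tests.

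**The plan's own figure.** The plan states 80% power for N = 60. A two-sided t test with 30 per group gives 62.8% at d = 0.60 and 73.6% at d = 0.68, so the 80% is not reproduced on that basis. That is a separate matter. The d comes from amphetamine mood data, and d = 0.60 is used here only for scale.

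**Bias in servings under an imbalance.** Bias = (difference in number of men / 30) x sex effect. For 18 v 13 men:
- 5/30 x 0.3 = 0.05 SD
- 5/30 x 0.5 = 0.083 SD, which is 0.083/0.60 = 14% of d = 0.60
- 5/30 x 0.8 = 0.133 SD

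**Type I error of the servings t test, 30 per group.** Each range runs across sex effects of 0.3 to 0.8 SD; the sex-adjusted model stays at about 5%.

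| Men, high v low | Unadjusted t test |
|---|---|
| 16 v 14 or 17 v 14 | 3.8% to 4.9% |
| 18 v 13 | 5.1% to 5.9% (5.4% at 0.5 SD) |
| 18 v 12, 0.8 SD only | about 7% |

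**Exact matching, 15 v 15, sex effect 0.5 SD.** Each subject lies 0.25 SD from the group mean because of sex. The expected pooled variance is therefore 1 + 60 x 0.25²/58 = 1 + 3.75/58 = 1.065. The t statistic shrinks by √1.065 = 1.032, so the critical value of 2.00 acts like 2.07 and type I error is about 4.3%; simulations gave 4.0% to 4.5%. Power at d = 0.60 is about 60.5% unadjusted and 62.8% with sex in the model, a difference of about 2 points.

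**Fewer subjects in the servings test.** The plan does not say whether placebo choosers enter it. With an assumed 20 alcohol choosers per group, type I error is 4.8% to 5.0% at 12 v 9 men and 5.2% to 5.8% at 12 v 8.

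**Alcohol choice.** With a 20-point sex difference (70% v 50%, or 80% v 60%), 18 v 13 men shifts the group difference by 5/30 x 20 = 3.3 points. Exact enumeration of type I error:

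| Men | Chi-square | Cochran-Mantel-Haenszel by sex |
|---|---|---|
| 15 v 15 | 4.3% to 4.4% | 4.8% to 5.0% |
| 18 v 13 | 5.2% | 4.8% to 4.9% |
| 18 v 12 | 5.5% to 5.6% | 4.9% |

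**How likely is a gap of 5?** With no steering and half men in each group, two Binomial(30, 0.5) counts differ by 5 or more in 24.5% of samples. Monitoring should make this rarer. If the matching check is an uncorrected chi-square (the plan does not say), 18 v 13 gives p = 0.20 and would not be flagged.

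**The case against.** The strongest reply is that sex is already controlled in the design. Monitoring meant to secure a match implies correcting it through recruitment, and unadjusted tests of groups matched by design are standard practice. At gaps of 2 or 3 men the t test shows no inflation. Even with no steering at all, type I error averaged over every possible imbalance is 4.9% to 5.05%. Inflation appears only conditional on a gap of about 5 or more. The documents give no link between sex and stop-task group, and no sex effect on choice. The Drugs paragraph also cites similar breath alcohol levels in men and women at the sex-adjusted dose, which closes one route to such an effect.

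All of this stands, and it limits the point to an optional improvement. It does not remove the point. Adjustment protects against a residual gap, recovers some power under exact matching if sex matters, and costs little if it does not.

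A reader might go further and infer that dose order is also a confounder of the choice tests. It is not: the drug given first is randomised, so leaving order out affects only precision. A reader might also infer an error from the absence of a stated action after the matching check. That is missing detail, and the text does not support calling it a flaw.

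**Conclusion.** The point holds as a minor, low-cost improvement. Sex is a covariate in the subjective-effect ANOVAs but is absent from both primary choice tests, in groups that are not randomised and that the protocol intends to match on sex. Carrying the adjustment over would make the plan consistent and slightly more robust.

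It would be wrong to conclude that the choice tests are invalid or that their type I error is materially inflated. Under an assumed 0.5 SD sex effect, the harm at a gap of 5 men is a shift of about 0.08 SD and a type I error of about 5.4%. The figure near 7% needs both a gap of 6 men and a 0.8 SD effect, and nothing in the documents supports an effect of that size. If matching works as intended, what remains is a slightly conservative test and about 2 points of power, again only if sex matters.

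**What to change.** In the Statistical analyses section, analyse number of servings with a linear model on group and sex, in the same subjects as the planned t test. Analyse alcohol choice with a Cochran-Mantel-Haenszel chi-square stratified by sex. Keep the plain t test and chi-square as supportive analyses. Dose order need not be added.

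No new data are needed, since sex is already recorded. If sex has no effect, adjusting is almost free when the groups are balanced (62.9% to 62.8% power at d = 0.60). At 18 v 13 men the variance of the group estimate rises by 1/(1 − r²), where r² = 1.67/60 = 0.028 (1.67 is the chi-square for group by sex). That is a factor of 1.029, and power falls from 62.8% to 61.4%. For choice (60% baseline, odds ratio 4, no sex effect), stratifying moves power from 62.5% to 62.8% at 15 v 15 men, and it is 60.8% at 18 v 13. The main choice result would be reported as a sex-stratified test instead of a plain chi-square.

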Initial reports have investigated associations between impulsive personality and response to alcohol. These suggest that individuals scoring higher on self-report measures of impulsivity also report greater stimulation and less sedation after drinking, and that this association is stronger at higher doses (Hendershot et al., 2013; Leeman et al, 2013). These promising new findings further emphasize the need to probe this association with a behavioral measure of impulsive action.

Study Aim: *To examine the degree to which impulsive action predicts rewarding effects of alcohol.* In this study we will examine the degree to which impulsive action predicts sensitivity to the rewarding effects of alcohol in healthy adults. To attain this objective, we will test the *working hypothesis* that individuals high in impulsive action, but matched on drinking history, will report significantly greater euphoria and arousal after alcohol than those low in

impulsive action, and that they will exhibit greater preference for alcohol over placebo in a choice test. We will test our working hypotheses by comparing individuals high and low in impulsive action in both subjective reward and choice for alcohol vs placebo. The primary measures of euphoria and arousal with alcohol will be BAES Stimulation (see below), as well as ARCI A (arousal) and MBG (euphoria), and DEQ Drug Liking. The measure of choice will be the choice for alcohol over placebo and the number of alcohol servings consumed on the last session. Successful completion of this study will provide important information regarding the degree to which poor inhibitory control is linked to alcohol reward, as measured by both subjective and behavioral measures. Taken together with our other concurrent study with amphetamine, it will also provide information about the generalizability of associations between poor inhibitory control (i.e., impulsive action) and drug reward. Further, evidence that individuals with poor inhibitory control are more sensitive to the rewarding effects of alcohol, a drug that is often co-abused with stimulant drugs, will set the stage for future studies to examine neurobiological substrates underlying poor inhibitory control and both stimulant and alcohol reward. This will provide valuable information regarding potential risk factors for poly-drug abuse in these individuals.

Research Design and Methods:

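### The stated 80% power for N=60 does not follow from d = .60–.68: with 30 per group the planned Group x Drug F-test has about 63–74% power

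*Combined protocol and SAP*

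**What the plan says.** The only sample-size justification is the Sample size determination paragraph of the combined protocol and SAP. It takes its effect size from preliminary d-amphetamine data, where between-group "t tests for subjective response measures of Elation and Vigor (AUC; 20 mg vs. placebo) suggest a medium effect size", given as d = .60–.68. It then says that N=60 "subjects would provide 80% power" at alpha = .05 for a difference between the high and low impulsive groups. It states neither the sidedness of the test nor a single design value of d.

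The Design paragraph splits the sample equally: one group with "stop reaction time > 325ms; N=30" and the other with "stop reaction time < 270ms; N=30".

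The Statistical analyses section plans a 2 (Group) x 2 (Drug) mixed ANOVA for each subjective measure, with dose order and sex as covariates. AUC is averaged over the two alcohol sessions and over the two placebo sessions. Post hoc tests follow on this condition: "If the overall F-test for the group X drug interaction is significant" at p < .05.

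On outcomes, the Study Aim says: "The primary measures of euphoria and arousal with alcohol will be BAES Stimulation", and adds ARCI A, ARCI MBG and DEQ Drug Liking. Elation and Vigor are not named there, in Design or under Measures. The Procedure section says only: "Mood and vital signs will be recorded every 30 minutes post-beverage administration", with no mood instrument named.

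**The concern.** For a two-group comparison with 30 per group, 80% two-sided power at the 5% level needs a standardised difference somewhat above 0.7. The plan quotes a range that ends at .68, so its 80% looked too high for its own inputs.

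Because no other justification for N is given, readers will use this figure to interpret a null result. If the interaction is not significant, a reader who believes the power was 80% will count that as stronger evidence against the hypothesis than the design can supply.

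A second, smaller matter is that the scales behind d are not among this trial's listed outcomes, and the plan does not say that a similar d is being assumed for the outcomes it does list.

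**Working it through.** **Inputs**

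- n = 30 per group (Design); N = 60 and alpha = .05 (Sample size determination).
- d = .60 to .68 (Sample size determination). It is a between-group difference in the drug-versus-placebo AUC contrast, so it is on the scale of the Group x Drug interaction.
- Planned test: the interaction F-test at p < .05 (Statistical analyses). With two groups and two drug conditions it has 1 numerator df. F equals the square of the t statistic comparing the groups on drug-minus-placebo differences, so the test is two-sided.

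**Method**

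The noncentrality is d × √(n/2) = d × √15 = 3.873d, with df = 60 − 2 = 58. Two-sided power is P(|T| > 2.002), where T is noncentral t with those parameters. One-sided power uses the critical value 1.672.

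**Can the plan's 80% be reproduced?**

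| d | Noncentrality | Two-sided power | One-sided power |
|---|---|---|---|
| .60 | 2.324 | 62.8% | 74.3% |
| .64 (midpoint) | 2.479 | 68.4% | 79.0% |
| .65 | 2.517 | 69.7% | 80.0% |
| .68 | 2.634 | 73.6% | 83.1% |

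Under the planned two-sided test, 80% is not reached at any d in the range. The one route that recovers it inside the range is a one-sided 5% test at d of about .65.

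**Cross-checks of the two-sided figures**

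- Noncentral F(1, 58) with noncentrality 15d² (5.40 and 6.94): 62.8% and 73.6%, identical.
- Two df spent on covariates that explain nothing, F(1, 56): 62.7% and 73.5%.
- Normal approximation: 64.2% and 75.0%.
- Simulation of the t-test on difference scores, 200,000 trials: 62.9% and 73.6%.

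**What 80% would need**

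- At 30 per group: d = 0.736 two-sided, or 0.650 one-sided.
- At d = .60, two-sided: 44.6, so 45 per group (N = 90).
- At d = .68, two-sided: 34.9, so 35 per group (N = 70).

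**Implied false-negative risk**

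1 − 0.736 = 0.264 and 1 − 0.628 = 0.372, so about 26–37% against the 20% that the plan implies.

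**Sensitivity to features for which the plan gives no figures**

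- *Covariates.* If they explain a share R² of the variance of the difference score, the F noncentrality becomes 15d²/(1 − R²). With 56 df, 80% needs R² of about .15 at d=.68 and .34 at d=.60.
- *Averaging two session pairs.* If the preliminary d came from one drug and one placebo session (not stated), d is multiplied by √(2/(1 + ρ)), where ρ is the correlation of difference scores between pairs. Then 80% needs ρ of at most about .71 at d=.68 and .33 at d=.60.

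**The case against.** The best defence is that 80% can be recovered. A one-sided 5% test at d=.65 needs 30 per group and gives 80.0%; the midpoint .64 gives 79.0%. The hypotheses are directional and the paragraph is silent on sidedness, so the figure may well have arisen this way. On that reading the fault is an undisclosed input that does not match the planned test, rather than a slip in calculation. That is a fair account of a possible origin, but it does not rescue the statement. No one-sided test is specified anywhere, a directional hypothesis does not make an F-test at p < .05 directional, d=.65 is not quoted, and the two endpoints that are quoted give 74% and 83% one-sided.

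It can also be said that the paragraph does not name the F-test. True, but its d is a between-group comparison of a drug-versus-placebo contrast, which is what the interaction tests.

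A third point is that session averaging could lift real power. At d=.68 and ρ of .5, .6 or .7, power would be 84.9%, 82.5% or 80.2%; at d=.60 and ρ=.5 it would be 75.1%. This stands as a limit on the conclusion: the documents cannot settle the true power. They do show that 80% is unsupported as written, since the paragraph relies on no such gain.

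Finally, the plan openly says that d comes from d-amphetamine data, and borrowing a d inherently assumes that it carries over. That is right. The point about Elation and Vigor is a matter of disclosure and would not justify a change on its own.

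**Conclusion.** The concern holds. For the test the plan specifies, with its own n, alpha and d, power is about 63–74%, and 80% requires d of about 0.74. The shortfall is roughly 6 points at the top of the range and 17 at the bottom.

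The result rests on two assumptions: that the preliminary d is taken unchanged as the d of this trial's contrast, and that no credit is given for averaging or covariates, for which the plan offers no figures. No dropout allowance is stated, and any loss of subjects would lower power further. The mismatch affects how a null result should be read. It does not bias an estimate or alter the type I error rate.

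**What to change.** Restate the power sentence along these lines: N=60 (30 per group) gives about 63–74% power at two-sided alpha = .05 for d = .60–.68, and the smallest effect detectable with 80% power is d of about 0.74.

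Add one sentence saying that the Elation and Vigor scales behind d are not among this trial's listed outcomes, so the figure applies to BAES, ARCI and DEQ only if a similar d is assumed.

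If 80% came from a one-sided test, a single design d, or an expected gain from averaging or covariates, state that input and its value. If it was a one-sided test, the mismatch with the planned F-test also has to be explained.

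The cost is the rewording of one paragraph and a less favourable stated power. N, outcomes, analyses and procedures need not change.
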